Current treated or untreated cancer*
Documented nutritional deficiencies (such as Beriberi, Pellagra, Rickets, Scurvy, Keshan Disease)*

*exclusion criteria for giving clozapine to neutropenic patients are similar to exclusion criteria for giving chemotherapy to BEN patients.

Smokers are permitted. All sites will pay careful attention to hospital admissions in smokers to ensure that the change in smoking status does not affect clozapine blood levels. Smoking is permitted at the hospital sites and blood levels should be drawn at the time of inpatient/outpatient change. This is just an extra precaution to ensure that changes in the amount and routine of smoking do not have large effects on clozapine optimization in these patients.

STUDY DESIGN AND METHODS:

- This is a single treatment group, open-label, prospective study. This study will take place at three sites; the Maryland Psychiatric Research Center (MPRC), University of Maryland School of Medicine, Howard University, and the Federal Neuropsychiatric Hospital Yaba, Lagos, Nigeria (FNPHY). The study will begin at the MPRC site and the other sites will come on board only when the studies and consents are fully approved at each site. We will notify the UMB IRB when each site is fully functioning.
- MPRC will be the lead site for regulatory compliance, coordination, design, leadership, data storage and analysis. The Nigerian site and Howard University both are well established research sites with ongoing NIH research and an enriched environment for clinical research. Patients will be enrolled for 9 months duration from a cohort of 250 African ancestry (African-American or Nigerian) subjects who have had evidence of neutropenia (ANC<2500 cells/mm³) in the past 24 months and are otherwise clozapine eligible.
- We will enroll a target of approximately 80 at MPRC, approximately 130 in Nigeria and approximately 40 at Howard University with a range of 70-90 at MPRC if needed, a range of 130-150 if needed in Nigeria and 40-50 at Howard if needed.

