Venous blood samples will be drawn to measure clozapine levels once during the titration phase (Day 14), or more often if needed during titration for clinical purposes, monthly during the 6-month clozapine treatment phase, and at the conclusion of the study. Levels will be obtained prior to the administration of the morning dose of clozapine. Samples will be analyzed using High Performance Liquid Chromatography (HPLC). Clozapine levels (clozapine, norclozapine) are sent out to LabCorp at the MPRC and Howard University site. At the MPRC these may also be sent to Saladax Biomedical, Inc, Bethlehem PA for immunoassay. HPLC equipment is budgeted for the Nigerian site so that all laboratory tests are done in the same lab to ensure standardization and QC. The purpose of the blood levels are 1) to ensure clozapine is being taken and 2) examine relationship of clozapine levels to ANC levels. Lab values that are considered to be abnormal may be repeated to verify accuracy. A corresponding capillary draw will occur at baseline, approximately week 4 and 8 to confirm it matches venous blood levels. This is optional and only offered at MPRC site with capillary tubes.

Other Laboratory and Metabolic Monitoring:

A chemistry panel (liver enzymes, BUN, creatinine, electrolytes, thyroid), and metabolic profile (lipids, fasting blood glucose) will be drawn at baseline and repeated monthly. All laboratory values outside normal ranges will be discussed and addressed with the medically accountable physician and clinical team at each site. A determination of

appropriate diagnostic procedures and/or follow up treatment will be made by the medically accountable physician. Lab values that are considered to be abnormal may be repeated to verify accuracy. We also will be collecting existing lab values if possible and will request only with patient permission for previous records. Cytokines labs will be drawn prior to the start of clozapine, and at the middle and endpoint of the clozapine trial.

INFECTION MONITORING:

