- Body temperature will be taken at each visit. Since clozapine treatment can raise the basal body temperature by up to 1 degree Fahrenheit, a slight increase in body temperature from pre-treatment baseline would not necessarily be indicative of infection. Fever is generally defined as an increase in body temperature to over 38.0 ° Celsius using a tympanic thermometer or to over 37.5 ° Celsius using an axillary thermometer. Fever is usually accompanied by sickness behavior, which may consist of lethargy, anorexia, sleepiness, hyperalgesia, and inability to concentrate. The medically accountable physician will obtain a history, conduct a review of systems, and perform a physical examination on any participant that develops a fever during the study. Because infection in neutropenic patients can proceed rapidly, a close initial evaluation is necessary and the medically accountable physician will promptly evaluate the seriousness and origin of the infection. As part of the fever workup, laboratory and radiological tests will be performed as deemed necessary.
- At each visit, participants will be asked about symptoms such as sore throat, mouth ulcers, flu-like symptoms, chills, rigors, arthralgia, or any other symptoms of infection. Participants will be instructed to contact the study physician immediately, if they develop any of these symptoms.
- A determination on study discontinuation, antiviral, antibiotic, antifungal, or, in Nigeria, antimalarial treatment will be made with the physician and infectious disease consultant as needed. The same criteria apply to all three sites. We will also pay special attention to clozapine levels and order a blood level during an infection as clozapine blood levels can rise.

SYMPTOM MONITORING:

- Psychiatric symptoms will be monitored at 2 times pretreatment to establish a baseline (approximately 6 weeks prior to clozapine start, and 1 week prior to clozapine start), and every four weeks thereafter during the six months of clozapine treatment.
- Decisions regarding response to clozapine and continuation of clozapine treatment will occur in collaboration with the treatment team.

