We will also collect data on WBC, ANC and demographic information on people previously treated in Maryland on a waiver system. Their data is available in clinical charts at Spring Grove Hospital and will only collect with approval from the hospital and the Spring Grove Research Committee. These patients will not be eligible to reenroll in this study but the data will be available to add to the study as it will help decrease the final sample size needed to enroll in the study. We will link this data from another study approval where a waiver of informed consent has been granted to study antipsychotic use (HP-00040084).

PRIMARY OUTCOME VARIABLES:

The primary outcomes are to measure ANC levels, side effects and patient safety.

STATISTICAL ANALYSES:

Analysis of Effect of clozapine on WBC and ANC levels: We will characterize variation of WBC and ANC levels in participants by *DARC* null genotype. We anticipate 212+ AA participants with BEN who are homozygous for the *DARC* null allele who will be the focus of this analysis, with other participants with BEN to be examined in a separate analysis. We will compute within-patient means and standard deviations of weekly WBC and ANC by three months intervals, starting with the three-month pre-treatment phase, and continuing for the six-months of follow-up on clozapine treatment, and observe the frequency of ANC values observed that exceed specific levels of concern (e.g. <500, <700, <1000 cells/mm³). We will estimate the change from baseline in overall average WBC and ANC during each three month interval after initiation of clozapine, and assess whether these change with time using a mixed model for repeated measures ANCOVA, controlling for baseline. Frequency of other events of concern (serious infection, need for treatment for very low ANC) will also be reported. We will also perform analyses of effects of mean participant pre-treatment ANC, clozapine dose and clozapine blood level on mean ANC during clozapine treatment and ANC<500 cells /mm³ during clozapine treatment, using linear and logistic regression. To date all published work and US guidelines are based on non-BEN samples and not specific to schizophrenia patients.

For the study when we report the results we will evaluate a subgroup of people with a history of ANC < 1500 cells/mm³

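### The regression of mean on-treatment ANC on clozapine level has no site term, so a site difference in both measures can bias the slope

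*Combined protocol and SAP*

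**What the plan says.** The Clozapine Blood Levels part of Laboratory Monitoring gives two purposes for the levels: confirming that clozapine is taken, and to "examine relationship of clozapine levels to ANC levels". The analysis is one sentence in Statistical Analyses (effect of clozapine on WBC and ANC levels). It opens with "We will also perform analyses of effects of mean participant pre-treatment ANC" and goes on to "clozapine dose and clozapine blood level on mean ANC during clozapine treatment and ANC<500 cells /mm³ during clozapine treatment, using linear and logistic regression". The outcome of the linear model is therefore one mean per participant. The plan does not say whether the three predictors enter jointly, or how several levels become one value.

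No site, laboratory or assay term appears in the statistical section. The one repeated-measures model, a "mixed model for repeated measures ANCOVA, controlling for baseline", concerns change over three-month intervals and is not described as including level.

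On measurement, "This study will take place at three sites". Levels go to LabCorp from the two US sites, with a possible additional immunoassay at MPRC, and "HPLC equipment is budgeted for the Nigerian site so that all laboratory tests are done in the same lab". ANC comes from Lab Corp or Athelas One in the US and from an on-site Beckman Coulter in Nigeria. A footnote to the Schedule of Events lets capillary 3-part counts take over from the 5-part CBC after 4 weeks in some instances. The schedule gives about seven levels per participant, alongside weekly ANC.

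**The concern.** With one point per participant, the slope compares participants with each other. About half of them are Nigerian, and their levels and counts come from different equipment from the US participants' values. Having all tests done in one laboratory holds within a site, not across the US and Nigeria.

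If one group has both higher measured levels and a different on-treatment change in ANC, for whatever reason, the regression attributes part of that contrast to clozapine level. Gaps in opposite directions can create an apparent fall in ANC with rising level. Gaps in the same direction can hide a real one. Either result would mislead on a question that the levels are collected to answer.

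**Working it through.** **Inputs from the documents.** Target enrolment by site is 80, 130 and 40 (Study Design and Methods), so the Nigerian share is 130/250 = 0.52. The plan's n after 15% dropout reproduces: 250 × 0.85 = 212.5, stated as 212. No alpha, power or effect size is given for this regression.

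**Assumed inputs (not in the documents).** Log level has SD 0.5 between and 0.3 within participants, with six monthly levels. Log ANC has SD 0.25 between and 0.25 within. The on-treatment shift in log ANC has SD 0.10. Log dose has SD 0.35 and acts one-to-one on log level. The Nigeria-US gap is dL in log level and dA in the on-treatment ANC shift, with no true level effect.

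**Bias without site or dose.** With p = 0.52, p(1−p) = 0.2496. The variance of a participant's mean log level is V = 0.5² + 0.3²/6 = 0.265. The expected slope is

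b = p(1−p)·dL·dA / (V + p(1−p)·dL²).

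- dL 0.3, dA 0.05: 0.003744 / 0.2875 = 0.013
- dL 0.3, dA 0.10: 0.007488 / 0.2875 = 0.026
- dL 0.5, dA 0.10: 0.01248 / 0.3274 = 0.038

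The standard error is about 0.020. In the middle case b/SE = 1.3, so P(Z > 1.96 − 1.3) is about 25%, in line with simulation.

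**Bias with dose in the model.** If the level gap comes from assay or metabolism, V falls to 0.265 − 0.35² = 0.1425. The three slopes become 0.003744/0.1650 = 0.023, 0.007488/0.1650 = 0.045 and 0.01248/0.2049 = 0.061. If the gap comes entirely from dosing, no gap in level remains once dose is held fixed, and b = 0.

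**Simulated false-positive rates (nominal 5%, 52% Nigerian).**

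| Model | dL 0.3, dA 0.05 | dL 0.3, dA 0.10 | dL 0.5, dA 0.10 |
|---|---|---|---|
| Level + pre-treatment ANC | 11% | 24–28% | 52–57% |
| Same, plus site | about 5% | about 5% | about 5% |

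With dose added but no site, the rate is about 5% in all three settings if dosing causes the level gap. It runs from 14% to 75% across them if assay or metabolism does. In the models of the table the standard error is 0.020 with or without site. With no site differences the regression without site is unbiased, with an error rate of about 5%.

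**Masking.** With a true slope of −0.05, dL 0.3 and dA 0.10 (dose not in the model), the expected slope without site is −0.05 + 0.026 = −0.024. Simulation gives the same value, with power of 21–23%, against 68–72% with site.

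**What pre-treatment ANC removes.** In a separate simulation with gaps of 0.5 within-site SD in both level and ANC (dose not modelled), the error rate is 13% without site or pre-treatment ANC. Adding pre-treatment ANC gives 7% if the whole ANC gap predates treatment, and 20% if it appears only on treatment. Site terms give about 5% in each case.

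**Within-participant slope.** Averaging reduces 6 × 212 = 1,272 scheduled pairs (7 × 212 = 1,484 with the extra first-month level) to 212 points. Under the main assumptions the within-participant slope has SE 0.0256. For a true slope of −0.05, 0.05/0.0256 = 1.95, so power is about 50%, below the 68–72% of the site-adjusted regression. In the separate simulation, without pre-treatment ANC, the order reverses (SE 0.031 within, 0.069 between). Which slope is more precise therefore depends on the assumptions.

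**Logistic model.** At the 0.9% one-year historical rate that the plan cites, 212 × 0.009 gives about 1.9 events, too few to rely on a site-adjusted fit.

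**The case against.** Four objections have weight. First, pre-treatment ANC and dose are both named as predictors. Entered jointly, they remove stable ANC laboratory offsets and level gaps caused by dosing. That stands, but joint entry is not stated, and neither removes an assay gap in level combined with an ANC gap that arises on treatment, for example from the capillary switch.

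Second, the White Blood Cell part of Laboratory Monitoring says that using different laboratories is not of concern. Its reason is that safety cutoffs are standardized, which does not make the counts interchangeable as a regression outcome.

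Third, levels are to be measured by HPLC, and the immunoassay is only an addition at one site. That narrows the assay difference but does not exclude one between laboratories.

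Fourth, the sizes are assumed. That is correct: the upper rates need a gap of 0.10 in the ANC shift, a full SD of that assumed shift.

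A reader might also infer that the within-participant comparison is free of site and assay and should replace the planned regression. The documents do not support this. ANC method can change within a participant after week 4. Infection can move both measures: the protocol tells staff to "order a blood level during an infection as clozapine blood levels can rise" and names infection as a possible cause of low ANC. The stated purpose does not favour a within-participant question over a between-participant one. Averaging the pairs is a choice with trade-offs, not an error in itself.

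**Conclusion.** The point holds as a conditional one: the planned regression lacks a site term that it needs if sites differ in both measured level and on-treatment ANC shift. Different laboratories and counters make such differences plausible, but the documents do not show or size them. Under the stated assumptions the nominal 5% error becomes about 11–57% without dose. With dose it stays near 5% or rises to 14–75%, depending on whether dosing or assay and metabolism cause the level gap. These ranges illustrate what could happen; they are not estimates of this trial's error rate. If there are no site differences, the planned slope is unbiased.

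This is a secondary analysis. A reader might infer that the agranulocytosis risk estimate is also in doubt; it uses neither clozapine levels nor this regression, and is unaffected.

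**What to change.** Add site (three levels) to the linear regression on mean ANC, and state that pre-treatment ANC, dose and level enter jointly and how each participant's levels are summarised. Use only scheduled pre-dose levels taken while on clozapine, from one assay type (HPLC). The restriction to time on clozapine is needed because the Withdrawal Criteria continue blood levels after clozapine stops. Add site to the logistic regression only if the number of ANC<500 events allows.

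As a supporting analysis, not a replacement, fit a mixed model of ANC at the scheduled level visits. Split log level into the participant's mean and the visit's deviation from it. Include week on clozapine, site, pre-treatment ANC, ANC method at that visit (venous or capillary), level assay and a participant random intercept. Repeat it without visits that have a recorded infection.

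The cost is analysis-plan wording and one extra model, with no new blood draws. Site adds essentially nothing to the standard error (0.020 either way). The downside of the supporting slope is lower precision under the main assumptions (0.026 against 0.020), and it remains open to ANC-method changes and infection.

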Vital Signs (heart rate, BP, temperature, and respiratory rate)	X	X (weekly)	X	X (weekly) (Twice during week 7 and then weekly)
BMI assessment	X		X	X (monthly) Visits 10,14,18,22,26,30)
EKG (USA only)	X		X	
BPRS, CGI, CDS (when possible 2 x pre clozapine start)		X	X	X (monthly) Visits 10,14,18,22,26,30)
Pregnancy test (Females)	X		X	X (monthly) Visits 10,14,18,22,26,30)
Side Effect Checklist	X		X (2 x this week)	X (weekly)
Questionnaire on clozapine blood draw preferences			X (or earlier)	X (week 2 and 4)
SAS, BAS, AIMS	X		X	X (monthly) Visits 10,14,18,22,26,30)
Clozapine Serum Level (venous and capillary) ***				X (2x for first month, monthly thereafter)
Retrospective Chart review				X

*this will change according to participant and monitoring parameters if ANC <1200 cells/mm³

** WBC/ANC capillary lab results (3 part differential) will be drawn each week and will superscede full CBC (5 part differential) after 4 weeks in some instances. CBC can also be drawn when PI or physician request. Weekly monitoring of either venous or capillary will be required weekly throughout the study.

*** capillary blood draw for clozapine level is optional at the MPRC site and performed three times, once at baseline, once at approximately week 4 and once at approximately week 8. This is a prick of the finger with maximum of 3 ml for each stick. This is separate from fingerstick for ANCs that are only a few drops of blood

LABORATORY MONITORING:

White Blood Cell (WBC) and Absolute Neutrophil Counts (ANC):

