Participants enrolled in the study at all 3 sites will receive the modified guidelines (table below) in addition to their informed consent and the investigator and patient will sign the consent acknowledging the modified guidelines. More stringent monitoring may take place if ANC levels fluctuate and modifications from this guideline may occur on a case by case basis with the consultation of a physician, hematologist and PI. During the study subjects will be very closely monitored as per below. Subjects will be educated concerning signs and symptoms of infection and the need to immediately report these throughout the study.

The Food and Drug Administration (FDA) has approved the modified monitoring procedures under an IND:

Absolute Neutrophil Count (ANC) Value	Modified Monitoring Plan Recommendation for Patients with History of or Current Benign Ethnic Neutropenia (BEN). Changes can be made with consultation from hematology. Always consider other medications that may be contributing to ANC suppression.
Clozapine Initiation	
 1. All patients initiating clozapine in the study will have had ANC <2500/mm³ in the past 24 months and those enrolled will not have a history of ANC<500/mm³. 2. Patients with two baseline ANC levels ≥1000/mm³ will be initiated with weekly blood draws. 3. Patients with baseline ANC levels between 500-999/mm³ may be initiated 
 a. After hematology consult and b. With specific oversight plan approved by hematology and study team. c. If initiated, patients will have ANC drawn twice weekly for first month of treatment prior to be considered for weekly monitoring. If ANC levels fall below 500/mm³, treatment will be interrupted as per protocol below. d. Justification for deviation from Risk Evaluation Management System (REMS) recommendations: We recognize that these are more lenient criteria than REMS, however, patients are enrolled in clinical trial with increased monitoring and we will be seeking a hematology consult and oversight prior to initiation and to make a plan for increased monitoring once treatment initiated.
ANC ≥1000/mm ³	Continue weekly ANC monitoring.

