Pharmacy and General Overall Guidelines	
 1. All US participants will be registered the clozapine REMS program prior to initiation of clozapine. 2. US participants will be registered as BEN patients and, if necessary, the REMS program will be apprised of modified guidelines. 3. Clozapine will be dispensed as a seven day supply, so long as the ANC is at least 1000 to coincide with recommended blood draws. For patients whose ANC is > 500/mm³ and < 1000/mm³, medications may be dispensed as a three or four day supply based on appointment dates or as indicated below*. 4. If clozapine needs to be discontinued, participants will be contacted by phone or in person and advised to stop medication and come in for a follow-up visit. 5. A centralized research designee (clinical pharmacist) will coordinate with the dispensing pharmacy (if different than centralized) and physician involved with participant to ensure PDA is available where needed (outpatients) or that eligibility criteria is provided (inpatients). The centralized research designee clinical pharmacist shall act as designee for pre-identified prescribers working in the study. Per these guidelines, after physician review and approval, these specialized designees shall enroll patients and enter ANC levels for the study. 
 a. Justification for this deviation from REMS guide: All treatment decisions will be made by the prescribing psychiatrist after review of ANC and clinical criteria. Our specially trained clinical pharmacist is part of the clinical research team with advanced expertise in treating BEN patients with clozapine so highly qualified to accurately enter this information into the REMS system.
Other Information	
*daily, weekly or twice weekly blood draw and dispensing (particularly in the range of <500-<1000 /mm³) will be determined based on additional recommendations from the FDA, REMS implementation or based on individual patient parameters. Patients that remain between 500-1000/mm³ for longer than 4 weeks may be recommended for weekly clozapine blood draws and dispensing. Also going from twice weekly to weekly monitoring should occur after 4 values are back above 1000 cells/mm³ Emergency supply of two doses is given to all patients.

A patient version to give out at time of consent is included at the end of the protocol.

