outlined in NIH NOT-MH-14-015 (<http://grants1.nih.gov/grants/guide/notice-files/NOT-MH-14-015.html>). This depository will allow other researchers access to data from this clinical trial, with the assurance that the participant's individual name or other identifying information will not be included in the data shared with other researchers.

WBC and infection monitoring:

All subjects in the study will be evaluated weekly during clozapine treatment for WBC and ANC. The team will closely examine any risk of severe neutropenia or infection. Twice weekly monitoring will be instituted in most cases when ANC drops below 1200 cells/mm³. The full procedure for WBC monitoring is in the protocol. In addition to monitoring by the PI and somatic physician, a expert hematology consultants are available to the research teams as well as the hematology team from the FDA at their request. Weekly temperatures will be taken and signs and symptoms of infection will be closely monitored.

We will notify the Data Safety Monitoring Board (DSMB) monitoring the study whenever a case of agranulocytosis occurs. The DSMB will review data on the accumulated cases to recommend whether to terminate the study, modify the ANC monitoring guidelines or take other action. If cases of agranulocytosis occur, the DSMB will review, based on the number of observed cases and the projected total sample size, whether the final estimated risk of agranulocytosis from this study in BEN subjects treated with clozapine using the guidelines described in this protocol is likely to be too high to warrant modification of clozapine treatment guidelines for BEN subjects.

Monitoring of adequate psychiatric symptom response:

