The participant may choose not to participate in this study. If he/she chooses not participate in this study, their treatment at any facility or clinic including MPRC and Spring Grove Hospital will not be affected. Their continued care and treatment will not change if they choose not to take part in this study.

PARTICIPANT COMPENSATION:

During the first 6 weeks participants will have approximately 8 (or fewer) visits for screening and blood draws. During the last 6 months participants will have approximately 24 visits. Participants will be compensated \$20 per visit for their time for a total of approximately \$640 for participation in the study if they complete approximately 8 months. If any portion is completed participants will be paid only for the visits they completed. Participants will be paid by cash or check monthly and will also provided transportation to and from visits as needed.

PATIENT MONITORING

Absolute Neutrophil Count (ANC) Value	Modified Monitoring Plan Recommendation. Modifications may be made for each patient with hematology consult. Must be given to patient at time of consent. Patient Name _____ Date received _____
ANC ≥1000/mm ³	Continue weekly WBC monitoring.
ANC <1000/mm ³ to ≥500/mm ³	1. No Interruption of therapy 2. Redraw WBC to ensure second ANC value within range 3. Twice weekly WBC monitoring 4. Return to once weekly WBC monitoring when > 1000 /mm ³

WBC=white blood count, ANC=absolute neutrophil count

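### At ANC 1000–1199 the protocol gives two default draw frequencies, and draws triggered by low counts inflate an all-draws tally of values below 1000

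*Combined protocol and SAP*

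**What the plan says.** Five places set weekly draws from 1000.

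- MONITORING GUIDELINES, Clozapine Initiation, item 2: "Patients with two baseline ANC levels ≥1000/mm³ will be initiated with weekly blood draws".
- The ANC ≥1000 row of the same table: "Continue weekly ANC monitoring".
- The row for 500–999, steps 5 and 6: twice weekly until the count is back at 1000 or the patient's known baseline, then weekly.
- Pharmacy and General Overall Guidelines, item 3: a seven-day supply "so long as the ANC is at least 1000 to coincide with recommended blood draws". The Other Information row adds that the step from twice weekly to weekly should follow four values back above 1000.
- The PATIENT MONITORING sheet handed over at consent, ANC ≥1000 row: "Continue weekly WBC monitoring".

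One place sets a different default. Under CONFIDENTIALITY AND PROTECTIONS AGAINST RISK, WBC and infection monitoring: "Twice weekly monitoring will be instituted in most cases when ANC drops below 1200 cells/mm³". The next sentence reads: "The full procedure for WBC monitoring is in the protocol".

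The SCHEDULE OF EVENTS footnote to the CBC line (Visit 6 and Visits 7–30) also carries 1200: "this will change according to participant and monitoring parameters if ANC <1200 cells/mm³". It names no frequency.

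STATISTICAL ANALYSES plans to report the "frequency of ANC values observed that exceed specific levels of concern", with 500, 700 and 1000 as examples. It does not say whether extra draws count.

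**The concern.** A participant at 1100 is on weekly draws by default under one set of texts and on twice-weekly draws by default under the other. The longest gap between draws is 7 days or 3–4 days accordingly. Investigator and patient sign for the table, while the section describing protections against risk promises closer follow-up in the same band.

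The analysis is touched as well. ANC is a primary outcome. Extra draws are taken when counts are low, so a tally over all draws depends on the monitoring rule as well as on the patient's counts. Sites using different triggers would record different numbers of low values from the same ANC pattern. LABORATORY MONITORING sets aside concern about different laboratories on the ground that cutoffs are standardized in the protocol; for 1000–1199 they are not.

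A lesser gap sits beside this. Items 2 and 3 do not say which governs a lead-in with two values of at least 1000 and another of 500–999, so it is unclear whether the hematology consult before the first dose is required.

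**Working it through.** **The texts side by side, for an ANC of 1000–1199**

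| Place | Threshold | Default draws |
|---|---|---|
| Initiation item 2; ANC ≥1000 row | 1000 | weekly |
| 500–999 row, steps 5–6 | 1000 or known baseline | weekly |
| Supply rule | 1000 | seven-day supply, so weekly |
| Patient sheet | 1000 | weekly |
| WBC and infection monitoring (risk section) | 1200 | twice weekly as the norm |
| Schedule footnote | 1200 | a change, with no frequency or direction |

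The conflict is between the first four lines and the fifth. The footnote repeats the 1200 figure but adds no rule.

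**Illustration of size**

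The plan has no figure of its own to reproduce, and it gives no ANC distribution. Assumptions: normal ANC, mean 1100, SD 200, independent draws, 26 weeks, one scheduled draw a week plus one mid-week draw while on twice-weekly monitoring. A participant enters twice-weekly monitoring on a value below the trigger and leaves after four consecutive values of at least 1000, under both triggers. The four values come from the Other Information row; that they must be consecutive is my reading.

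1. P(ANC < 1000) = Φ((1000 − 1100)/200) = Φ(−0.5) = 0.3085. P(ANC < 1200) = Φ(0.5) = 0.6915. The chance that one value lies in the disputed band is 0.6915 − 0.3085 = 0.383.
2. Scheduled draws only: 26 × 0.3085 = 8.0 values below 1000, whatever the trigger.
3. Simulated draws per participant: 42.7 (trigger 1000) and 47.8 (trigger 1200), a difference of 5.1.
4. Whether a draw is taken depends only on earlier values, so with independent draws the expected number below 1000 is draws × 0.3085: 42.7 × 0.3085 = 13.17 and 47.8 × 0.3085 = 14.75.
5. Effect of the trigger: 14.75/13.17 = 1.12. Effect of counting all draws instead of scheduled ones: 13.17/8.02 = 1.64 and 14.75/8.02 = 1.84.

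Over means 1100–1200, SD 100–200 and weekly correlation 0 or 0.6, the 1200 trigger records about 8–46% more values below 1000. The top of that range is at mean 1200, SD 100, with independent draws, where the scheduled expectation is only 26 × Φ(−2) = 26 × 0.0228 = 0.6 values. If leaving twice-weekly draws under the 1200 trigger also needs four values of at least 1200, the excess is roughly 10–80%.

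**Limits of the illustration**

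SD 200 at mean 1100 is wide. P(ANC < 700) = Φ(−2) = 0.0228, so 1 − (1 − 0.0228)^26 = 45% of participants would have at least one weekly value below 700, while RISKS AND DISCOMFORTS expects none. The model omits immediate redraws and the known-baseline exit. At mean 1500, SD 200 the chance of a value in the band is Φ(−1.5) − Φ(−2.5) = 0.06, so participants well above 1200 are little affected.

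**The case against.** The strongest reply is that the documents already show which text governs. MONITORING GUIDELINES says participants are monitored according to its table and that FDA approved those procedures. The sentence with 1200 is a summary in a risk section and at once refers the reader on: "The full procedure for WBC monitoring is in the protocol". Stricter monitoring is allowed case by case, so extra draws at 1000–1199 break no rule. This favours the table, but it does not settle the default. The discretion clause names no 1200 trigger, and allowing exceptions is different from stating what usually happens.

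On the analysis, the planned means and SDs are of weekly values, and the threshold frequencies stand in the same sentence. A weekly basis is therefore a natural reading. It is not stated, and one line would settle it. With independent draws the share of draws below 1000 is the same under either trigger; it is the count that moves.

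Three stronger readings are tempting and should not be drawn:

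- That the schedule footnote itself orders closer draws below 1200. It says only that the schedule will change according to the monitoring parameters.
- That the trigger shifts about ten draws per participant. If participants left twice-weekly draws at the first value at or above the trigger, the same illustration would give 34.0 against 44.0 draws and 10.5 against 13.6 low values, an excess of 29%. That ignores the written step-down after four values above 1000.
- That the agranulocytosis estimate or its confidence limits are compromised. Nothing in the conflict reaches them.

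On the lead-in, item 3 can be read to cover any baseline value of 500–999, and the first value below 1000 on treatment brings hematologist contact and twice-weekly draws in any case. That makes the gap minor.

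**Conclusion.** The point holds as a contradictory safety threshold: for ANC 1000–1199 the protocol makes weekly draws the default in its table and patient sheet, and twice weekly the default in its risk section. The table has the better claim, but a site could follow either text in good faith.

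The statistical consequence is modest. Under the stated assumptions the choice of trigger changes the count of values below 1000 by about 12% at mean 1100, SD 200, and by 8–46% over the range examined. Counting triggered draws at all matters more in the main illustration: about 13–15 recorded values against 8.0 on scheduled draws. These sizes rest on an assumed distribution and cannot be checked from the documents; the textual conflict needs none of them. It should be corrected, and doing so is cheap.

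**What to change.** **Trigger.** Make the monitoring table the only source. In the SCHEDULE OF EVENTS footnote and in WBC and infection monitoring, replace the 1200 wording by *as in the monitoring table*. This changes wording only and can go into the next IND and IRB amendment.

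If hematology and FDA prefer 1200, every place that now uses 1000 for draw frequency must move together: item 2, the ANC ≥1000 row, steps 5–6 of the 500–999 row, the supply rule, the four-value step-down and the patient sheet. Changing only some of them would create a new conflict. The cost is more draws for participants whose counts run near 1000–1200.

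**Analysis.** Add to STATISTICAL ANALYSES: *The frequency of ANC values below 1000 is based on the one scheduled draw per week; the frequency over all draws, including redraws and extra monitoring draws, is given as a second line.* State which sample counts when a capillary and a venous sample are both taken, as the schedule foresees in the first four weeks of treatment. No further data are needed, and the first figure then does not depend on the trigger a site used.

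**Lead-in (minor).** Subject to hematology's agreement, add to item 2: *If any lead-in ANC is 500–999/mm³, item 3 applies.* This can only add consults before the first dose.
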